## **9.6 Concomitant medications**

All medications received during the treatment period will be considered as concomitant medications and will be coded by WHO medical dictionary; patients who received concomitant medications will be listed.

# **10. QUALITY CONTROL AND QUALITY ASSURANCE**

During study conduct, periodic monitoring performed by the Imperial College Trials Unit will ensure that the protocol and GCPs are being followed. An independent data committee and the Imperial 'INFORM' database will aid in this process. The committee may review source documents to confirm that the data recorded on CRFs is accurate. The investigator and Imperial College will allow the appropriate regulatory authorities direct access to source documents to confirm this verification if necessary. The study site may be subject to review by the institutional review board (IRB)/independent ethics committee (IEC), and/or to quality assurance audits performed. It is important that the investigator(s) and their relevant personnel are available during the monitoring visits and possible audits or inspections and that sufficient time is devoted to the process.

## **11. DATA HANDLING AND RECORD KEEPING**

### **11.1. Case Report Forms / Electronic Data Record**

As used in this protocol, the term case report form (CRF) should be understood to refer to either a paper form or an electronic data record on the Imperial INFORM database or both. A CRF is required and should be completed for each included subject.

The investigator has ultimate responsibility for the accuracy, authenticity, and timely collection and reporting of all clinical, safety, laboratory data entered on the CRFs and any other data collection forms. The CRFs must be signed by the investigator or by an authorized staff member to attest that the data contained on the CRFs is true. Any corrections to entries made in the CRFs, source documents must be dated, initialled and explained (if necessary) and should not obscure the original entry.

In most cases, the source documents are the hospital's or the physician's subject chart. In these cases data collected on the CRFs must match the data in those charts. In some cases, the CRF, or part of the CRF, may also serve as source documents. In these cases, a document should be available at the investigator's site and clearly identify those data that will be recorded in the CRF, and for which the CRF will stand as the source document.

### **11.2. Record Retention**

To enable evaluations and/or audits from regulatory authorities, the investigator agrees to keep records, including the identity of all participating subjects (sufficient information to link records, e.g., CRFs and hospital records), all original signed informed consent forms, copies of all CRFs, serious adverse event forms, source documents, and detailed records of treatment disposition, and adequate documentation of relevant correspondence (e.g., letters, meeting minutes, telephone calls reports). The records should be retained by the investigator according to ICH, local regulations, or as specified in the Clinical Study Agreement, whichever is longer.

If the investigator becomes unable for any reason to continue to retain study records for the required period (eg, retirement, relocation), the study records must be transferred to a designee acceptable to the sponsoring institution, such as another investigator. The investigator must obtain the sponsors written permission before disposing of any records, even if retention requirements have been met.

## **12. ETHICS**

### **12.1. Independent Ethics Committee & NHS R&D approval**

It is the responsibility of the investigator to have prospective approval of the study protocol, protocol amendments, Molecular Profiling Supplement, informed consent forms, and other relevant documents, e.g., recruitment advertisements, if applicable, from the IEC/NHS R&D. All correspondence should be retained in the Investigator File.

The only circumstance in which an amendment may be initiated prior to IEC/NHS R&D approval is where the change is necessary to eliminate apparent immediate hazards to the subjects. In that event, the investigator must notify the IEC/NHS R&D and Sponsor in writing immediately after the implementation.

## **12.2. Ethical Conduct of the Study**

The study will be conducted in accordance with the Declaration of Helsinki on Ethical Principles for Medical Research Involving Human Subjects, adopted by the General Assembly of the World Medical Association (1996).

In addition, the study will be conducted in accordance with the protocol, the International Conference on Harmonisation guideline on Good Clinical Practice, and applicable local regulatory requirements and laws.

## **12.3. Subject Information and Consent**

All parties will ensure protection of subject personal data and will not include subject names on any sponsor forms, reports, publications, or in any other disclosures, except where required by laws. The informed consent form must be in compliance with ICH GCP, local regulatory requirements, and legal requirements. The informed consent form used in this study, and any changes made during the course of the study, must be prospectively approved by both the IEC/NHS R&D before use.

The investigator must ensure that each study subject, or his/her legally acceptable representative, is fully informed about the nature and objectives of the study and possible risks associated with participation. The investigator, or a person designated by the investigator, will obtain written informed consent from each subject or the subject's legally acceptable representative before any study-specific activity is performed. The investigator will retain the original of each subject's signed consent form.

## **12.4. Reporting of Safety Issues and Serious Breaches of the Protocol or ICH Good practice**

In the event of any prohibition or restriction imposed (i.e., clinical hold) by an applicable Competent Authority in any area of the World, or if the investigator is aware of any new

information which might influence the evaluation of the benefits and risks of the investigational product, Imperial College and Pfizer should be informed immediately.

In addition, the investigator will inform Imperial College and Pfizer immediately of any urgent safety measures taken by the investigator to protect the study subjects against any immediate hazard, and of any serious breaches of this protocol or of ICH GCP that the investigator becomes aware of.

## **13. DEFINITION OF END OF TRIAL**

### **13.1. End of Trial**

End of Trial is defined as the time at which:

- Enrolment is completed according to protocol planned sample size, and assessments and requirements are completed as per protocol.
- The stated objectives of the trial are achieved.

## **14. SPONSOR DISCONTINUATION CRITERIA**

Premature termination of this study may occur because of Imperial College sponsor decision, regulatory authority decision, change in opinion of the IRB/IEC, drug safety problems, or at the discretion of Pfizer. In addition, Pfizer retains the right to discontinue development of Axitinib in patients with advanced metastatic colorectal cancer whose disease has progressed on/after or are intolerant to one prior anti-angiogenic therapy at any time.

## **15. PUBLICATION OF STUDY RESULTS**

### **15.1. Communication of Results by Pfizer**

Pfizer fulfils its commitment to publicly disclose the results of studies through posting the results of this study on ClinicalStudyResults.org. Pfizer posts the results of studies that fall into either of the following categories:

- Studies that Pfizer registered on [www.clinicaltrials.gov](http://www.clinicaltrials.gov), (ClinicalTrials.gov) regardless of the reason for registration; OR
- All other studies for which the results have scientific or medical importance as determined by Pfizer.

For studies involving a Pfizer product, the timing of the posting depends on whether the Pfizer product is approved for marketing in any country at the time the study is completed:

- For studies involving products already approved in any country and for studies that do not involve a Pfizer product, Pfizer posts results within one year after study completion, defined as last subject, last visit (LSLV)
- For studies involving products that are not yet approved in any country, Pfizer posts the results of already-completed studies within one year after the first regulatory approval of the product
- For studies involving products whose drug development is discontinued before approval, Pfizer posts the results within one year after such discontinuation

Pfizer's posting on ClinicalStudyResults.org includes the following elements:

- Protocol title, study phase, and indication
- A link to approved product labelling, if applicable
- The synopsis of study results
- Citations of known study publications
- Legal disclaimer

The study results synopsis posted on ClinicalStudyResults.org (called the PhRMA website synopsis) uses the format established by the ICH-E3 Clinical Study Report (CSR) Synopsis. If posting of study results to ClinicalStudyResults.org jeopardizes a planned publication of the study results, a Pending Full Publication notice is substituted for the synopsis until the study results publication has issued or two years have elapsed, whichever occurs first.

Pfizer posts citations only for publications that are accessible in recognized (searchable) publication databases. Single-centre results publications for a multi-centre study are generally not posted because they may not accurately reflect the results of the study.

## **15.2. Publications by Investigator**

Pfizer has no objection to publication by Investigator in conjunction with the sponsor, Imperial College of any information collected or generated by Investigator, whether or not the results are favourable to the Investigational Drug. However, to ensure against inadvertent disclosure of Confidential Information or unprotected Inventions, Investigator will provide Pfizer the opportunity to review any proposed publication or other type of disclosure before it is submitted or otherwise disclosed.

Investigator will provide manuscripts, abstracts, or the full text of any other intended disclosure (poster presentation, invited speaker or guest lecturer presentation, etc.) to Pfizer at least 30 days before they are submitted for publication or otherwise disclosed. If any patent action is required to protect intellectual property rights, Investigator agrees to delay the disclosure for a period not to exceed an additional 60 days. Investigator will, on request, remove any previously undisclosed Confidential Information (other than the Study results themselves) before disclosure.

For all publications relating to the Study, Institution will comply with recognized ethical standards concerning publications and authorship, including Section II - "Ethical Considerations in the Conduct and Reporting of Research" of the Uniform Requirements for Manuscripts Submitted to Biomedical Journals, <http://www.icmje.org/index.html#authorship>, established by the International Committee of Medical Journal Editors.

Publication of study results is also provided for in the Clinical Study Agreement between Pfizer and the institution. In this section entitled Publications by Investigators, the defined terms shall have the meanings given to them in the Clinical Study Agreement.

## Appendix 1 Required laboratory tests

Laboratory Test	Conventional Units	Conversion Factor	SI Units
Hematology			
hemoglobin (Hgb)	g/dL	x 10	µg/L
platelet count (Plt)	10  /mm 	x 10 	10  /L
white blood count (WBC)	10  /mm 	x 10 	10  /L
white blood cell differential	%	x 0.01	fraction
Chemistry			
total bilirubin	mg/dL	x 17.1	mmol/L
alanine transaminase (ALT)	U/L	N/A	U/L
aspartate transaminase (AST)	U/L	N/A	U/L
alkaline phosphatase	U/L	N/A	U/L
gamma-glutamyl-transpeptidase (GGT)	U/L	N/A	U/L
lactate dehydrogenase (LDH)	U/L	x 0.016667	µkat/L
total protein	g/dL	x 10	g/L
albumin	g/dL	x 10	g/L
sodium	mEq/L	x 1.0	mmol/L
chloride	MEq/L	x 1.0	mmol/L
potassium	mEq/L	x 1.0	mmol/L
calcium	mg/dL	x 0.25	mmol/L
phosphate	mg/dL	x 0.323	mmol/L
blood urea nitrogen (BUN)	mg/dL	x 0.357	mmol/L
creatinine	mg/dL	x 88.4	µmol/L
glucose	mg/dL	x 0.055	mmol/L
TSH	µU/mL		
free T3	pg/dL		
free T4	pg/dL		
Hepatocellular carcinoma tumor marker			
α-Fetoprotein	ng/mL	x 1.0	µg/L
HBV panel, HCV antibodies			
HBsAg, HBe and anti-HBc	N/A		
Anti-HCV antibodies	N/A		
Coagulation			
Prothrombin Time (or INR)	secs (or NA)	N/A	secs (or NA)
Urinalysis			
Urine protein, glucose, blood	N/A	N/A	N/A

## **AXMUS-C Principal Investigator**

### **Trial summary**

AXMUS-C (AXitinib Monotherapy Ultrasound in Colorectal cancer) is a double blind, randomised, 2 arm, phase II trial to identify if responders to Axitinib have greater overall survival than Axitinib non-responders and the placebo groups. Both arms commence with 8 weeks of either Axitinib monotherapy or placebo. Response will be judged using an imaging biomarker called the contrast enhanced ultrasound hepatic perfusion index.

Axitinib is a tyrosine kinase inhibitor against vascular endothelial growth factor receptors. It is administered orally at an initial dose of 3mg b.d. which can be titrated upwards to a maximum dose of 10mg b.d..

50 patients with metastatic colorectal cancer who are fit for Axitinib chemotherapy will be randomised at the start of chemotherapy to receive **initially**:

**Arm 1: Daily Axitinib** treatment for 8 weeks (2/3rds of patients)

*OR*

**Arm 2: Daily placebo** treatment for 8 weeks (1/3rd of patients)

[figure not shown]
The primary outcome measure will be overall survival in the patients whose liver blood flow measured by a special ultrasound test is changed by Axitinib. Secondary outcome measures include progression-free survival, overall response rate and toxicity.

## Appendix 5 Liver Ultrasound Protocol

The contrast agent used is SonoVue (Bracco SpA, Milan, Italy), which consists of a phospholipid shell containing the inert gas sulphur hexafluoride. The agent is prepared immediately prior to the examination by mixing 25 mg of the lyophilised powder with 5 ml of saline. 2.4 ml of the preparation is injected as an intravenous bolus via an antecubital vein.

After 4 hours of fasting, DCE-US scan is performed on each subject in the supine position using an iU22 ultrasound scanner (Philips Healthcare, Andover, MA) with a C5-1 curvilinear transducer. The probe is held still in the right intercostal space in order to visualise the porta hepatis. This allows simultaneous visualization of the hepatic artery (HA) and portal vein (PV) at a low mechanical index (0.06) imaging with non-linear pulse sequence in the form of power modulated pulse inversion. A 1 minute contrast/B-mode side-by-side cine loop is recorded with data acquisition starting immediately after the contrast bolus injection. A reading from a control artery (carotid or femoral) is taken to confirm the input function of the test. Cine loops are then transferred to a workstation for analysis.

QLAB software (Philips Healthcare, Andover, MA) is used to quantify contrast dynamics in the HAP and PV. Raw linear DICOM data is used for analysis. Regions of interest of equivalent sizes (5mm^2) are drawn over the HA and PV lumens. Time-intensity curves are obtained by computing the mean intensity of pixels comprised within the regions of interest against time. An example analysis is presented below:

**Figure 3: Time-intensity curve for hepatic artery (yellow), portal vein (red) using QLab software. Both have had modelling curves fitted to smooth the data. The calculated values for the DCE-HPI are shown in the box.**

TICs are fitted using a least square algorithm based on the Nelder-Mead method (Matlab, The MathWorks, Natick, MA) with a local density random walk function described by:

$$I(t) = AUC \frac{e^{\lambda}}{\mu} \sqrt{\frac{\mu}{(t-t_0)}} \frac{\lambda}{2\pi} \exp\left\{-\frac{1}{2}\lambda\left(\frac{\mu}{(t-t_0)} + \frac{(t-t_0)}{\mu}\right)\right\} + I_0$$

AUC is the area under the curve,  $I^{-1}$  is the skewness of the curve,  $m$  is the travel time between the entry and exit sites of the ROI at the carrier fluid velocity,  $t_0$  is the bolus arrival time, and  $I_0$  is the baseline intensity offset. Peak intensity (PI) which correlates with blood volume is defined as max, rise time (RT) is defined as the time taken for the intensity to increase from 5% of PI to 95% of PI, and wash-in slope (WIS) which correlates with blood flow rate. PI and WIS were derived from HA and PV TICs and dynamic contrast-enhanced hepatic perfusion index (DCE-HPI) which reflects the ratio of hepatic arterial to portal venous blood flow to the liver is defined as:

$$DCE - HPI = \frac{PI[HAP].WIS[HAP]}{PI[PV].WIS[PV]}$$

## Appendix 6 RECIST Tumour Assessment Criteria (Version 1.1)

The determination of efficacy during this study will be based on objective tumour assessments made according to the RECIST system of unidimensional evaluation.

### Measurability of Tumour Lesions

At baseline, individual tumour lesions will be categorized by the investigator as either measurable or non-measurable by the RECIST criteria as described below.

#### Measurable:

Tumour lesion: Must be accurately measured in at least one dimension (longest diameter in the plane of measurement is to be recorded) with a minimum size of:

- 10 mm by CT scan (CT scan slice thickness no greater than 5 mm).
- 10 mm caliper measurement by clinical exam (lesions which cannot be accurately measured with calipers should be recorded as non-measurable).

Malignant lymph nodes: To be considered pathologically enlarged and measurable, a lymph node must be >15mm in short axis when assessed by CT scan (CT scan slice thickness recommended to be no greater than 5 mm). At baseline and in follow-up, only the short axis will be measured and followed.

**Non-Measurable:** All other lesions, including small lesions (longest diameter <10mm or pathological lymph nodes with >10 mm to <15 mm short axis) as well as truly nonmeasurable lesions. Lesions considered truly non-measurable include: leptomeningeal disease, ascites, pleural or pericardial effusion, inflammatory breast disease, lymphangitic involvement of skin or lung, abdominal masses/abdominal organomegaly identified by physical exam that is not measurable by reproducible imaging techniques.

NOTE: If measurable disease is restricted to a solitary lesion, its neoplastic nature should be confirmed by cytology/histology.

### Recording Tumour Measurements

All measurable lesions up to a maximum of 2 lesions per organ and 5 lesions in total representative of all involved organs should be identified as **target lesions** and measured and recorded at baseline and at the stipulated intervals during treatment. Target lesions should be selected on the basis of their size (lesion with the longest diameters) and their suitability for accurate repetitive measurements (either by imaging techniques or clinically).

The longest diameter will be recorded for each target lesion. The sum of the longest diameter for all target lesions will be calculated and recorded as the baseline sum longest diameter to be used as reference to further characterize the objective tumour response of the measurable dimension of the disease during treatment. All measurements should be performed using a caliper or ruler and should be recorded in metric notation in centimeters.

All other lesions (or sites of disease) should be identified as **non-target lesions** and should also be recorded at baseline. Measurements are not required and these lesions should be followed as “present” or “absent.”

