### **Definitions of Tumour Response**

#### **Target Lesions**

**Complete response (CR)** is defined as the disappearance of all target lesions. Any pathological lymph nodes (whether target or non-target) must have reduction in short axis to <10 mm.

**Partial response (PR)** is defined as a >30% decrease in the sum of the longest dimensions of the target lesions taking as a reference the baseline sum longest dimensions.

**Progressive disease (PD)** is defined as a >20% increase in the sum of the longest dimensions of the target lesions taking as a reference the smallest sum of the longest dimensions recorded since the treatment started, or the appearance of one or more new lesions. In addition to the relative increase of 20%, the sum must also demonstrate an absolute increase of at least 5 mm.

**Stable disease (SD)** is defined as neither sufficient shrinkage to qualify for PR nor sufficient increase to qualify for PD taking as a reference the smallest sum of the longest dimensions since the treatment started.

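### Appendix 6 gives nodal target lesions two incompatible measurement rules, so the same scans can be scored as progressive or as stable disease

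*Combined protocol and SAP*

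**What the plan says.** **Nodes.** Appendix 6, *Measurable*, accepts a malignant node above 15 mm in short axis as measurable and adds: "At baseline and in follow-up, only the short axis will be measured and followed".

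**Targets and the sum.** Appendix 6, *Recording Tumour Measurements*, draws targets from the measurable lesions without separating nodes ("All measurable lesions up to a maximum of 2 lesions per organ and 5 lesions in total"). For the individual lesion it says "The longest diameter will be recorded for each target lesion". For the total, the rule is "The sum of the longest diameter for all target lesions will be calculated and recorded as the baseline sum longest diameter". The purpose given for this baseline figure is "to be used as reference to further characterize the objective tumour response of the measurable dimension of the disease during treatment".

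**Response categories.** Under *Definitions of Tumour Response, Target Lesions*, PD "is defined as a >20% increase in the sum of the longest dimensions of the target lesions". The comparator for that increase is fixed by the words "taking as a reference the smallest sum of the longest dimensions recorded since the treatment started". There is also an absolute condition: "the sum must also demonstrate an absolute increase of at least 5 mm". PR and SD use the same longest-dimension sum. Complete response (CR) instead requires nodes, target or not, to fall below 10 mm on the short axis. *Determination of Best Overall Response* repeats the since-treatment-started reference for PD.

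**Timing and use.** Baseline imaging is a screening procedure before treatment (Section 6.1). CT or MRI follows every 8 weeks (Section 7.1). The Trial Summary and Section 3 sort patients into CR/PR/SD or PD at week 8. Section 9.1 makes progression-free survival (PFS) by RECIST the primary endpoint.

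**The concern.** A reader who follows the nodal rule has no longest diameter to put into the sum. A reader who follows the summing rule breaks the nodal rule. Nothing in the appendix says which prevails. Nodes can clearly be targets: the CR definition refers to target nodes, and inclusion criterion 1 admits measurable lesions outside the liver.

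What is at stake is the date of progression. Section 9.1 ties the next step to a PFS gain of more than 6 weeks. Scans are 8 weeks apart, so one call moved by one scan shifts that patient's PFS by more than this margin. The week-8 category also matters for the ultrasound index: Section 2.1 groups SD with CR and PR as responders, so a patient switched between PD and SD changes sides in that comparison and in the ROC analysis of Section 9.2.

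Separately, a PD reference that counts only sums recorded after treatment began would, taken word for word, leave the week-8 scan with nothing to be compared against.

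**Working it through.** The plan gives no figure to reproduce here. Lesion sizes and growth rates below are assumptions. The PD rule (more than 20% and at least 5 mm) is from Appendix 6.

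**1. The same scans under the two rules.**

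| Assumed lesions | Short axis for the node | Longest diameter for the node |
|---|---|---|
| A. Liver 30 to 40 mm; node 16 x 28 mm, unchanged | 46 to 56: 56/46 = 1.217, +21.7%, +10 mm, **PD** | 58 to 68: 68/58 = 1.172, +17.2%, **SD** |
| B. Liver 40+30 to 46+36 mm; node 16 x 28 to 22 x 30 mm | 86 to 104: +20.9%, +18 mm, **PD** | 98 to 112: +14.3%, **SD** |
| C. Liver 40+30 to 44+33 mm; node 16 x 28 to 18 x 42 mm | 86 to 95: +10.5%, **SD** | 98 to 119: +21.4%, +21 mm, **PD** |

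With no nodal target the two sums are identical.

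**2. Which way the error runs.** Let the non-nodal sum be N at baseline and grow by d. Let the node have short axis s and longest diameter l, both growing by a fraction g. The relative PD criterion becomes:

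- short axis: d + g·s > 0.2(N + s), that is d − 0.2N > (0.2 − g)s
- longest diameter: d − 0.2N > (0.2 − g)l

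Because l exceeds s, the longest diameter makes PD harder to reach when the node grows by less than 20% and easier when it grows by more. In case A, d − 0.2N = 10 − 6 = 4, which exceeds 0.2 x 16 = 3.2 but not 0.2 x 28 = 5.6.

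**3. How often.** Simulation of 200,000 records per row, one liver target and one node. Assumed: liver lesion 15–60 mm, node short axis 15–25 mm, long/short ratio 1.2–1.8 (all uniform), liver growth normal with mean 20% and SD 20%.

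| Assumed node growth (mean, SD) | PD, short axis | PD, longest diameter | PD lost + PD gained |
|---|---|---|---|
| 5%, 10% | 34% | 28% | 5.8% + 0.2% |
| 20%, 20% | 50.3% | 50.2% | 2.8% + 2.7% |
| 35%, 20% | 64% | 68% | 1.1% + 4.9% |

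About 6% of patients with such targets change category at one scan. The net direction depends on the assumed nodal growth. If 20–50% of the 50 patients had a nodal target (assumption), that is 10 x 0.06 = 0.6 to 25 x 0.06 = 1.5 patients per scan.

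**4. The reference for PD.** Assume sums of 100, 130, 150 and 160 mm at baseline and weeks 8, 16 and 24.

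- Baseline counted: 130/100 = +30%, PD at week 8.
- Taken word for word: no reference at week 8; 150/130 = +15.4% at week 16, not PD; 160/130 = +23.1% at week 24, PD.

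The second reading cannot be the intended one. It would make a PD call on target growth impossible at week 8, where the Trial Summary and Section 3 ask for one, and *Recording Tumour Measurements* makes the baseline sum the reference for objective response. PD by new lesions or non-target progression is unaffected either way.

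**The case against.** The nodal rule is the specific one and says only the short axis is measured. A careful reader would follow it, would have no long axis to sum, and would take the body's citation of RECIST version 1.1 (Sections 6.2 and 7.1) as settling the matter. The rule is the same in both arms of a double-blind trial, so no between-arm bias follows, and the number of patients affected may be very small.

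Much of this stands. No bias between arms is shown, and on the assumptions above the count is about one patient per scan. But Appendix 6 is headed as this trial's statement of the version 1.1 criteria, so citing that version does not resolve a conflict inside the appendix. The recording rule covers every target lesion without exception. Someone following the nodal rule still has to depart from the sum on which PR, PD and SD are defined.

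On the reference scan the objection succeeds against the stronger reading. A reader might infer that baseline is excluded and that target growth cannot count as PD at week 8. No section says so, and the week-8 classification and the stated role of the baseline sum point the other way.

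**Conclusion.** The nodal contradiction is real and lies in the rule that dates the primary endpoint. For a patient with a nodal target the same scans can be PD under one rule and SD under the other. Under the simulation's assumptions this happens in about 6% of such patients at a given scan; with no nodal targets it does not happen. The overall size cannot be fixed, because the documents do not give the share of patients with nodal targets.

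The omission of baseline from the PD and SD reference needs clarifying and is secondary.

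Three stronger inferences are not supported:

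- **That the nodal error always hides progression.** It does so on balance only if nodes grow more slowly than the 20% threshold; cases A and C go opposite ways.
- **That half or more of patients are mis-scored at week 8.** With the 6–8 week PFS of Section 9.1 taken as an exponential median, 1 − 2^(−8/8) = 50% to 1 − 2^(−8/6) = 60% would have an event by week 8 at that rate. This is only a ceiling on exposure to a literal reading that the plan does not intend. It includes deaths, new lesions and non-target progression, and it describes the conventional outcome in this cohort, not axitinib patients.
- **That a literal reading would cost at most one 8-week interval.** The example in step 4 gives 16 weeks, so no such bound holds.

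**What to change.** All changes are in Appendix 6.

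1. *Recording Tumour Measurements*: amend both the per-lesion sentence and the sum. Record the longest diameter for non-nodal targets and the short axis for nodal targets, and define the total as the *sum of diameters (longest diameter for non-nodal, short axis for nodal target lesions)*.
2. *Definitions of Tumour Response, Target Lesions*: use that term throughout in place of the sum of longest dimensions.
3. In the PD and SD definitions, and in *Determination of Best Overall Response*, state the reference as *the smallest sum of diameters recorded on study, including baseline*.

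The second sentence under change 1 and the repeat under change 3 must not be missed, or a new inconsistency is left behind. The cost is wording only: no extra scans or measurements and no change to the sample size. If any scans have already been read, check which diameter was recorded for nodal targets and re-derive the sums where needed.
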